12.4.2. Analysis of the Secondary Endpoints in Part B

HINE Motor Milestone Responders

The difference in the proportion of responders between treatment groups will be compared using logistic regression with the number of motor milestones at Baseline, age at symptom onset, and disease duration at Screening as covariates. Should the number of responders be less than 5 in either group, Fisher's exact test will be used instead. If Fisher's exact test is used, the unconditional confidence interval for the difference in response rates will be provided [Santner and Snell 1980].

The proportion of HINE Section 2 motor milestone responders will be assessed at Day 183 for 50/28 mg versus sham.

Total HINE Section 2 – Motor Milestones

Change from baseline to Day 183 for 50/28 mg versus sham and change from baseline to Day 302 for 50/28 mg versus 12 mg will be analyzed using the same methodology as described for the primary endpoint.

Plasma Neurofilament

For plasma NF-L, if the baseline assessment is missing, then the first available assessment post dose within Day 2 will be used instead as baseline.

Values that are BLQ will be set to half of the diluted LLOQ.

Change in plasma NF-L from (ratio to) baseline to Day 183 will be analyzed for 50/28 mg versus sham, and change in plasma NF-L from baseline to Day 29 will be analyzed for 50/28 mg versus 12 mg using the same method as for the primary endpoint.

CHOP-INTEND

Change in CHOP-INTEND from baseline to Day 302 will be analyzed for 50/28 mg versus 12 mg using the same methodology as described for the primary endpoint.

Time to Death or Permanent Ventilation

Permanent ventilation is defined as tracheostomy or ≥ 16 hours of ventilation/day continuously for > 21 days in the absence of an acute reversible event (Appendix A).

An independent EAC will determine, in a blinded fashion, the date at which a participant is considered to have met the definition of an event. The procedures for reviewing and adjudicating events will be described in a charter.

The time to death or permanent ventilation (tracheostomy or ≥ 16 hours of ventilation/day continuously for ≥ 21 days in the absence of an acute reversible event) and time to death (overall survival) will be analyzed using the log-rank test stratified by disease duration at Screening. The null hypothesis is that the comparison groups (ie., sham and 50/28 mg dose) have the same "survival" function. Participants who do not meet the endpoint definition will be censored at the last occasion the participant was seen (either in-person visit or by telephone contact), irrespective of whether the participant has completed the full course of treatment and whether the participant has completed the study or permanently withdrawn. The exception is time to death or permanent ventilation in cases in which a participant has begun a ventilator diary, in which case the latest entry in the diary will be used as the date of censoring. The proportion of participants meeting an event at timepoints of interest will be estimated using the Kaplan-Meier method.

The analysis will also be perfored for the comparison of sham versus 50/28 mg doses and the comparison of 12 mg versus 50/28 mg doses.

Time to Death

Overall survival will be analyzed in the same way as time to death or permanent ventilation.

[figure not shown]
Table 8 summarizes the planned statistical testing.

Table 8: Primary and Secondary Endpoints

Rank	Endpoint and Comparison	Analysis Method	Comparison of higher dose (50/28 mg) to
1	Change in CHOP-INTEND from baseline to Day 183 total score	Joint rank using MI	CS3B Matched Sham Control
2	Proportion of HINE Section 2 motor milestone responders at Day 183	Logistic regression or Fisher's Exact Test	CS3B Matched Sham Control
3	Change from baseline to Day 183 in HINE Section 2 total score	Joint rank using MI	CS3B Matched Sham Control
4	Change from baseline to Day 183 in plasma NF-L from baseline to Day 183	Joint rank using MI	CS3B Matched Sham Control
5	Change from baseline to Day 302 in CHOP-INTEND total score	Joint rank using MI	232SM203 12 mg Control
6	Change from baseline to Day 302 in HINE Section 2 Motor Milestones total score	Joint rank using MI	232SM203 12 mg Control
7	Change from baseline to Day 29 in plasma NF-L	Joint rank using MI	232SM203 12 mg Control
8	Time to death or permanent ventilation	Log-rank test stratified by disease duration at Screening	CS3B Matched Sham Control
9	Time to death	Log-rank test stratified by disease duration at Screening	CS3B Matched Sham Control
10	Time to death or permanent ventilation	Log-rank test stratified by disease duration at Screening	232SM203 12 mg Control
11	Time to death	Log-rank test stratified by disease duration at Screening	232SM203 12 mg Control

12.4.3. Analysis of the Remaining Endpoints

For Parts A, B, and C, summary statistics will be presented to characterize the efficacy data over time. For continuous endpoints, the summary statistics will generally include the number of participants with data, mean, standard deviation, median, minimum, and maximum. For categorical endpoints, the summary statistics will generally include the number of participants with data and the percentage of those with data in each category. Frequency distributions will be presented as appropriate. The change from baseline to each visit will be summarized. The number of hospitalizations will be analyzed using the rate at which they occur, and the time on a ventilator will be provided in the Statistical Analysis Plan.

12.6. Methods of Analysis for Pharmacodynamic Endpoints

The analysis population for PD will include all participants with available PD data.

Plasma and CSF NF-L levels will be summarized using available results. The baseline concentrations and the actual score and change (including absolute and percentage) will be presented by visit. In addition, the correlation between the baseline level and measurements, including weight, disease duration, and age at the first dose, will be presented.

For Part B, plasma NF-L and CSF NF-L levels will be analyzed as secondary endpoints (Section 12.4.2).

12.7. Methods of Analysis for Biomarkers/Pharmacogenetics

Plasma and CSF samples (collected as specified in Section 1.3) may be assayed for NF-L and data will be summarized using descriptive statistics and will be presented by dose group.

Sampling for this analysis will be approved at the discretion of each site's ethics committee. If a site's ethics committee does not approve the sampling for the analysis, this section will not be applicable to that site.

12.8. Methods of Analysis for Safety Endpoints

The analysis of safety will be performed separately for the Safety Set for Part A, Part B infantile-onset, Part B later-onset, and Part C. In addition, the Part B participants will be presented by treatment group. The duration of treatment and the amount of study treatment will be summarized.

12.8.1. Adverse Events

AEs will be coded using the Medical Dictionary for Regulatory Activities.

The incidence of treatment-emergent AEs and SAEs will be presented for Parts A, B, and C. All AEs will be analyzed based on the principle of treatment emergence. An AE will be regarded as treatment-emergent if it was present prior to receiving the first dose of nusinersen and subsequently worsened in severity or was not present prior to receiving the first dose of nusinersen but subsequently appeared.

The number and percentage of participants who experienced SAEs, AEs, and discontinuation from nusinersen due to an AE will be summarized. Additionally, AEs will be summarized by severity and relationship to nusinersen.

A participant having the same AE more than once will be counted only once in the incidence for that event. The occurrence of the AE with the greatest severity will be used in the calculation of incidence by severity; the occurrence of the AE with the strongest relationship to nusinersen will be used in the calculation of incidence by relationship to nusinersen.

AEs will be further tabulated by subgroup (e.g., age, race, sex, administration status of nusinersen [90-day intervals], and SMA history).

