All participants in Part C will receive a single bolus dose of 50 mg (which should be administered 4 months \pm 14 days after their most recent maintenance dose of 12 mg) followed by 2 maintenance doses of 28 mg on Days 121 and 241. Participants in Part C will remain at the clinic for at least 24 hours after the first (bolus) dose for the purpose of completing study assessments.

See Figure 1 for a schematic of the study design.

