- 4. Able to complete all study procedures, measurements, and visits and parent(s) or legal guardian(s)/participant has adequately supportive psychosocial circumstances, in the opinion of the Investigator
- 5. Must be compliant with the study travel policy (see Section 15.4)
- 6. Meets age-appropriate institutional criteria for use of anesthesia/sedation, if use is planned for study procedures (as assessed by the Investigator and either anesthesiologist or pulmonologist)
- 7. All female participants of childbearing potential (defined as any female physiologically capable of becoming pregnant) and all male participants of reproductive age must practice contraception as described in Section 11.5

Participants with SMA symptom onset ≤ 6 months (≤ 180 days) of age (infantile onset)

- 8. Age > 1 week to ≤ 7 months (≤ 210 days) at the time of informed consent
- 9. SMN2 copy number = 2
- 10. Onset of clinical signs and symptoms consistent with SMA at ≤ 6 months (≤180 days) of age
- 11. At Screening, receiving adequate nutrition and hydration, in the opinion of the Investigator
- 12. Body weight in at least the third percentile for age using appropriate country-specific guidelines
- 13. Gestational age of 37 to 42 weeks for singleton births and 34 to 42 weeks for twins. Infants with a lower gestational age may be considered for enrollment if there are no complications due to prematurity and approval by the Medical Monitor has been granted.

Participants with SMA symptom onset > 6 months (> 180 days) of age (later onset)

- 14. Onset of clinical signs and symptoms consistent with SMA at > 6 months (> 180 days) of age
- 15. Age 2 to < 10 years at the time of informed consent
- 16. Can sit independently but has never had the ability to walk independently
- 17. HFMSE score \geq 10 and \leq 54 at Screening
- 18. Estimated life expectancy > 2 years from Screening, in the opinion of the Investigator

Part C

All Participants

- 1. Signed informed consent of parent or guardian and signed informed assent of the participant, if indicated per participant's age and institutional guidelines
- 2. Currently on nusinersen treatment at the time of Screening, with the first dose being at least 1 year prior to Screening
- 3. Genetic documentation of 5q SMA (homozygous gene deletion, mutation, or compound heterozygote)

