6.3.2. Retesting and Rescreening

During the Screening period, participants who have an out-of-range result may be retested 1 time only at the discretion of the Investigator within the Screening process, without the need for a repeat full Screening. The Screening period may be extended for up to 10 days for individuals who cannot complete the Day 1 Visit within 21 days of signing the ICF, as long as they continue to meet other eligibility criteria.

Participants who fail Screening (see Section 6.3.3) may be rescreened once at the discretion of the Investigator. Participants who are rescreened will be assigned a new identification number.

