11.3. Monitoring and Recording Events

11.3.1. Adverse Events

Any AE experienced by the participant between the time of signing of the ICF and the last study visit/telephone contact is to be recorded on the CRF, regardless of the severity of the event or its relationship to study treatment. At each study visit, the Investigator will assess the participant for AEs and will record any new AEs or updates to previously reported AEs on the CRF.

AEs that are ongoing when the participant completes or discontinues the study will be followed by the Investigator until the event has resolved or become stable. AE outcome will be recorded on the CRF, as applicable.

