12.3. Definition of Baseline

The baseline for all assessments except CHOP-INTEND is defined as the last nonmissing assessment prior to the first dose of study treatment. The baseline for CHOP-INTEND is defined as the average of the assessments taken during the Screening/Baseline period.

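### The treatment-emergence rule in Section 12.8.1 is anchored to the first nusinersen dose, which in Part C precedes the study by at least a year; read literally, it counts Screening adverse events as emergent on the higher dose

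*Protocol*

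**What the plan says.** Section 12.8.1 of the protocol applies the rule to all three parts: "The incidence of treatment-emergent AEs and SAEs will be presented for Parts A, B, and C". An AE is treatment-emergent on either of two grounds. The first is that "it was present prior to receiving the first dose of nusinersen and subsequently worsened in severity". The second is that it "was not present prior to receiving the first dose of nusinersen but subsequently appeared". Both limbs use the same anchor, and no separate anchor is given for Part C.

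Part C inclusion criterion 2 (Section 6.1) requires each participant to be "Currently on nusinersen treatment at the time of Screening, with the first dose being at least 1 year prior to Screening". The first dose in this study comes later: "All participants in Part C will receive a single bolus dose of 50 mg" (Section 5.1), on Day 1.

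Section 11.3.1 has any AE "between the time of signing of the ICF and the last study visit/telephone contact is to be recorded on the CRF", so events before the bolus are collected. Screening in Part C lasts 21 days (Section 5.2), and Section 6.3.2 adds: "The Screening period may be extended for up to 10 days".

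Section 4 lists the incidence of AEs, including SAEs, among the primary endpoints of Parts A and C. Section 3.1.1 gives the purpose of Part C as evaluating the safety of moving from the approved regimen to the higher one.

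**The concern.** The rule works where participants have never had nusinersen, because the first nusinersen dose and the first study dose are then the same. In Part C they are at least a year apart. A participant in Screening is still on 12 mg. An AE starting then, and absent before the first-ever dose, meets the new-event limb before any higher dose has been given. The worsening limb has a related fault: it compares severity with the state before the first-ever dose, not the state just before the bolus.

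At stake is a primary endpoint of Part C, a descriptive estimate of AE incidence after the switch. The literal rule would assign some events on the old regimen to the new one. Part C has no concurrent control group that would carry the same error.

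**Working it through.** No stated figure in the protocol depends on this rule, so there is none to reproduce. The check applies the rule to each part and then measures the window affected.

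**Step 1: where the two anchors differ**

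| Part | Earlier nusinersen | First nusinersen dose = first study dose? |
|---|---|---|
| A | Excluded (Section 6.2, Part A criterion 13: prior ASO treatment) | Yes |
| B | Excluded (Section 6.2, Part B criterion 10: prior ASO treatment) | Yes |
| C | Required (Section 6.1, Part C criterion 2) | No, at least 1 year apart |

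Only Part C is affected, with up to approximately 40 participants.

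**Step 2: classification of a Part C event with onset in Screening**

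| Event | Literal 12.8.1 | Day 1 anchor |
|---|---|---|
| Absent before first-ever dose, unchanged after bolus | Emergent | Not emergent |
| Absent before first-ever dose, worse after bolus | Emergent | Emergent |
| Already present before first-ever dose, no worse since | Not emergent | Not emergent, unless worse after bolus |

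The first row is where the rule gives the wrong result.

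**Step 3: share of the AE-recording window that precedes the bolus**

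The Part C durations in Section 5.2 add up: 21 + 1 + 240 + 61 = 323 days to Day 302, and 21 + 1 + 240 + 120 = 382 days to Day 361. The part from Day 1 onward is therefore 302 or 361 days. Share = S / (S + follow-up), where S is the length of Screening. Footnote 1 of Tables 3 and 4 provides for a Screening visit within 7 days before Day 1, so S = 7 serves as a short case. S = 21 is the standard maximum and S = 31 the extended maximum.

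| S (days) | To Day 302 | To Day 361 |
|---|---|---|
| 7 | 7/309 = 2.3% | 7/368 = 1.9% |
| 21 | 21/323 = 6.5% | 21/382 = 5.5% |
| 31 | 31/333 = 9.3% | 31/392 = 7.9% |

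These are shares of time. They become shares of AEs only if the AE rate is constant across Screening and a period with three intrathecal doses, which the protocol gives no basis for.

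**Step 4: effect on incidence, by assumption**

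Assume an event type that occurs at one per participant-year. The proportion with at least one event is 1 − exp(−days/365).

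- Day 1 anchor, to Day 302: 1 − exp(−302/365) = 56.3%
- Literal rule, S = 7: 1 − exp(−309/365) = 57.1%; 0.8 points, about 0.3 of 40 participants
- Literal rule, S = 21: 1 − exp(−323/365) = 58.7%; 2.4 points, about 1 of 40
- Literal rule, S = 31: 1 − exp(−333/365) = 59.8%; 3.5 points, about 1.4 of 40

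**The case against.** The strongest reply is that the protocol elsewhere uses these words for the study dose. The Safety Set in Section 12.2 is everyone who receives nusinersen, defined separately for Part C; taken literally, it would include Part C screen failures. Section 5.1 calls the bolus the first dose in Part C, Section 5.2 defines Day 1 as the date of first dose, and Part C exclusion criterion 10 counts 12 months from the participant's first dose in the same sense. AE records also begin at consent, so the study holds no AE record of the state before a dose given a year earlier. This stands as evidence of intent: the Day 1 dose was very probably meant. It does not repair the wording. Section 12.8.1 names nusinersen and names Part C, and inclusion criterion 2 uses the first dose for the earlier one. An SAP may settle the anchor, but the protocol states this rule itself.

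The reply is also right that the consequence is limited. Part C is open-label with a single regimen, its sample size is not statistically based (Section 12.11), and no Part C test appears in Table 8. The error would overstate AE incidence, not hide it.

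Four stronger readings are tempting, and the documents support none of them.

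- A reader might infer that events before and after the switch cannot be told apart. Section 11.6.1 has the investigator determine onset and resolution dates, and the Day 1 date is known.
- A reader might see a contradiction with Section 12.3, which uses "the last nonmissing assessment prior to the first dose of study treatment". That section defines baseline for assessments, a different concept from AE emergence. It shows that suitable wording exists, no more.
- A reader might suppose that every Screening AE becomes emergent. A condition already present before the first-ever dose would still have to worsen.
- A reader might suppose that the whole previous year on 12 mg is swept in. Recording starts at consent, so new onsets are limited to Screening; an event already ongoing at consent matters only if it is recorded as an AE.

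**Conclusion.** The point holds as a wording error with a small, descriptive effect. One of the three parts that Section 12.8.1 names gets a wrong classification if the rule is programmed as written, and no other section redefines the AE anchor for Part C. The affected share of the recording window to Day 302 runs from about 2% to 9.3% according to the length of Screening. The participant counts rest on an assumed constant rate of one event per year. The definitional fault rests on neither assumption. The bias is toward a higher AE incidence on the 50/28-mg regimen. No result in Part A or Part B changes.

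**What to change.** In both limbs of the definition in Section 12.8.1, replace the first dose of nusinersen with the first dose of study treatment in this study (Day 1), which in Part C is the 50-mg bolus. Add that AEs with onset from ICF signing to the Day 1 dose are listed separately as pre-treatment, and count as emergent only if they worsen after that dose.

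The cost is one amended sentence, one added sentence and the matching derivation. No new data are needed, since onset dates are already collected. Part C incidence may fall slightly compared with the literal rule; Parts A and B stay the same.

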12.8.2. Clinical Laboratory Results

Clinical laboratory evaluations, including coagulation, hematology, blood chemistry, and urinalysis parameters, will be summarized using shift tables, presenting changes relative to each parameter's normal range. Summary statistics for actual values and changes from baseline will also be presented.

12.8.3. Vital Signs

The analysis of vital signs will focus on clinically significant abnormalities. Changes from baseline in vital signs and ECGs will be summarized.

12.8.4. Neurological Examinations

Changes from baseline in neurological examinations will be summarized.

12.10. Interim Analyses

Interim and final analyses for Parts A and C may occur prior to completion of Part B of the study.

An interim analysis of the primary endpoint in Part B may be performed when all participants with infantile-onset SMA have had the opportunity to reach the Day 183 visit.

Full details of the analyses and controlled access to the unblinded data will be documented in the Statistical Analysis Plan, the unblinding plan, and the IDMC charter.

12.11. Sample Size Considerations

A total sample size of approximately 145 participants is planned for this study (Table 9). The justification for the sample size for the infantile-onset SMA population in Part B is detailed as follows. The sample sizes for the remaining groups are not based on statistical considerations.

A minimum of 6 participants with later-onset SMA will be enrolled in Part A to characterize the safety, tolerability, and of a 28/28-mg dose of nusinersen (28-mg loading dose; 28mg maintenance dose). A total of 24 participants with later-onset SMA will be randomized to the Control Group and 50/28-mg Group in Part B in a ratio of 1:2; this will allow the exploration of the safety, tolerability, and efficacy of the 50/28 mg dose of nusinersen in this population. A total of up to approximately 40 participants will be enrolled in Part C (i.e., up to approximately 20 participants each in Cohorts 1 and 2) to characterize the safety, tolerability, and of a 50/28 mg dose of nusinersen in participants transitioning from maintenance dosing at the currently approved dose of 12 mg of nusinersen.

Table 9: Number of Participants in Each Study Part, by Symptom Onset

Part/Dose	Number of Participants		
	Later Onset	Infantile Onset	Total
Part A (28-mg loading dose; 28-mg maintenance dose)	6		6
Part B			
Control Group (12-mg loading dose; 12-mg maintenance dose)	8	25	33
50/28-mg Group (50-mg loading dose; 28-mg maintenance dose)	16	50	66
Part C (50-mg loading dose; 28-mg maintenance dose)			401
Total			145 ¹

The sample size is an estimate that may be up to approximately the stated number.

For the infantile-onset SMA population in Part B, a sample size of approximately 50 participants in the 50/28-mg Group and at least N= 20 sham participants from CS3B will provide at least approximately 99% power for the primary endpoint to detect an improvement of 24 points on CHOP-INTEND and 23% survival rate benefit (compared to that observed in Study CS3B participants receiving sham control) at Day 183 based on the joint-rank test at a 2-sided significance level of 0.05. This power calculation is based on simulations using data generated from a joint model of survival and functional change. The model used a difference of 24 points for the Day 183 change from baseline in CHOP-INTEND total score (50/28-mg Group — Study CS3B Sham Control Group) and a population standard deviation of 8.8 for change from baseline.

A secondary endpoint for this study is that the efficacy in the 50/28 mg Group compared to the 12 mg Control Group will be different based on the change from baseline to Day 302 in CHOP-INTEND.

For Part B, the randomization will be stratified as follows:

- For participants with infantile-onset SMA by disease duration: ≤ 12 weeks and > 12 weeks (time from age at symptom onset to age at informed consent)
- For participants with later-onset SMA by age at informed consent: < 6 years and ≥ 6 years

For Cohort 1 of Part C, an attempt will be made to enroll at least 8 but no more than 12 participants \geq 18 years of age (participants \geq 18 years of age must be ambulatory). For Cohort 2 of Part C, all participants must be \geq 18 years of age and can be either ambulatory or nonambulatory.

